6.3 Duration of Study Treatment

- 9 The number of days study treatment is delivered will be summarised by treatment group using
- 10 descriptive statistics. Summaries by treatment group will also be prepared for the proportion
- receiving treatment for at least 1 week, and proportion receiving treatment for at least 2 weeks.

6.4 Morbidity-Free Survival to Hospital Discharge (Primary Endpoint)

- 13 The primary analysis will be a comparison between treatment groups on the proportion of babies
- 14 experiencing the primary composite endpoint that is tested using a Wald test (with a χ_1^2 distribution)
- 15 from a log-binomial model fitted using generalised estimating equations to accommodate possible
- 16 correlation of data between siblings from multiple births. If the log-binomial model does not
- 17 converge, a logistic model will be used.

18 19

8

12

- A multiple imputation approach will be used to account for missing primary endpoint data in a
- 20 sensitivity analysis. The effect of assuming all missing values are uniformly indicative of an 'event'
- 21 (pessimistic scenario) or of 'no event' (optimistic scenario) may also be explored.

22

25

- 23 Estimates of the treatment effect on the primary endpoint that are adjusted for stratification factors
- and adherence to assigned treatment will be produced using the methods detailed in Section 8.

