6.5 Analysis of Categorical Secondary Endpoints

- 26 Secondary categorical endpoints include: survival to hospital discharge (Section 2.2), brain injury
- 27 (Section 2.3), NEC (Section 2.4), LOS (Section 2.5), RoP (Section 2.6), chronic lung disease (Section
- 28 2.9), and survival and development status at 24-36 months corrected gestational age (Section 2.11).

29

- 30 Secondary categorical endpoints will be analysed using the same modelling approach applied to the
- 31 primary endpoint (i.e. a log-binomial model fitted using generalised estimating equations to
- 32 accommodate possible correlation of data between siblings from multiple births. If the log-binomial
- 33 model does not converge, a logistic model will be used).

- 35 Sensitivity analyses will be undertaken on the categorical morbidity endpoints (i.e. brain injury, NEC,
- 36 LOS, RoP, and chronic lung disease) in which any missing values due to death are treated as an
- 37 event. An analysis of survival to 36 weeks may also be undertaken as a sensitivity analysis. Estimates
- 38 of the treatment effect on survival to hospital discharge that are adjusted for adherence will be
- 39 produced using the methods detailed in Section 8.2 in a sensitivity analysis.

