6.7 Safety Data Analysis

A descriptive analysis of SUSAR data will be conducted by treatment allocation. The event rate is expected to be low, and thus an exact test would be an appropriate choice to perform any formal comparisons between the two groups in the proportion experiencing a SUSAR.

7 Subgroup Analyses

Consistency of the treatment effect on the primary endpoint across subgroups will be tested by including a treatment-by-subgroup interaction term (along with the relevant main effect terms) as covariates in the analysis model (as specified in Section 6.4).

The subgroups of interest are: (i) birthweight <1000 g versus 1000-1499 g; (ii) randomised ≤72 hr versus >72 hr from birth; (iii) those who received versus did not receive probiotics by 36 weeks corrected gestation (note: this is a post-baseline covariate); (iv) ≤ 28 weeks versus >28 weeks gestation at birth. Because 'probiotic use by week 36' is a post-baseline covariate, an unbiased evaluation of its role as an effect-modifier will be attempted by categorising participating sites (NICUs) into tertile subgroups according to their propensity to use probiotics, and evaluating consistency of the treatment effect across these sub-groups.

Adjusted Analyses

8.1 **Stratification Factors**

Sensitivity of results obtained from the primary analysis of the primary endpoint to adjustment for stratification factors will be explored by included them as covariates in the model (See Section 6.4).

4 5 6

7

8

9

10

11

14

15

16

1

2

3

- Randomisation is stratified by gender, birth weight (<1000 g vs ≥1000-1499 g), according to whether the baby is from a single or multiple birth, and site (NICU). Given the modest number of patients at some sites, and the degree of variation in the number of babies recruited across sites (i.e. minimum is less than 10 babies and the maximum is more than 200 babies), sites will be categorised into larger groups that have a comparable pooled primary endpoint event rate. This will be done by estimating, in a blinded fashion, the event risk at each site pooled across treatments, and deriving 'risk classification' according to tertiles. Risk classification will be used as the covariate in the
- 12

13 adjusted analyses in preference to 'individual site'.

8.2 **Treatment Compliance**

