An overall treatment adherence adjusted estimate of the effect of bLF on (i) the primary composite endpoint and (ii) survival to hospital discharge will be calculated by dividing the estimated relative risk reduction (RRR) by the adherence rate as per the equation below.

17 18

$$\label{eq:RRR} \text{RRR}_{\text{adjusted}} = \frac{\text{RRR}}{100\% - (\text{bLF nonadherence \%}) - (\text{PBO nonadherence \%})}$$

19 20

The non-adherence percentage in each arm is defined as the proportion receiving less than two weeks of allocated treatment for reasons other than death.

21 22 23

24

25

26

27

A second approach for deriving treatment adherence adjusted estimates will involve clustering sites achieving comparable adherence rates into tertiles, calculating the treatment effect for each tertile, deriving a weighted combination of these individual estimates where the weights reflect the degree of adherence achieved for the tertile, and combining the treatment effect within each tertile (estimated using the analysis approach specified in Section 6.4) with its corresponding adherence weight to derive a weighted estimate.

28 29

The adherence weight (w_i) for the i^{th} tertile comprising k sites with n_i babies per site is: 30

31

$$w_i = \frac{\sum_{j=1}^{k} \{n_j \times \left(\% \ Adherence_j\right)\}}{\sum_{j=1}^{k} n_j}$$

The weighted estimate, on a log_e scale, (G) is: 32

$$G = \frac{\sum_{i=1}^{3} w_i \times \log_e(RR_i)}{\sum_{i=1}^{3} w_i}$$

The variance (V) of G will be calculated as: 33

$$V = \frac{\sum_{i=1}^{3} w_i^2 \times \text{Var}(\ln(RR_i))}{(\sum_{i=1}^{3} w_i)^2}.$$

The point estimate and 95% CI will be reported as e^G and $e^{G\pm 1.96 \times \sqrt{V}}$ respectively. 34

9 Synthesis of Trial Evidence

- 2 The evidence from LIFT will be placed in broader context in the primary reporting of results by
- 3 combining, where feasible, with evidence from other sources as described below.

4 9.1 Cochrane review

- 5 Consistent with the recommendation that reports of clinical trials should begin and end with an up-
- 6 to-date systematic review of all available randomized evidence, 5,6 data from this trial will be used to
- 7 update the most recent peer-reviewed Cochrane systematic review of trials of lactoferrin
- 8 supplementation in preterm infants. This will involve deriving an updated meta-analysis estimate of
- 9 the effect of lactoferrin on late onset sepsis, necrotizing enterocolitis and all-cause mortality, to be

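### The logistic fallback turns a risk ratio into an odds ratio with no step back; the realistic exposure is the stratification-adjusted model in SAP Section 8.1

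*SAP*

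**What the plan says.** Section 6.4 takes the primary Wald test "from a log-binomial model fitted using generalised estimating equations to accommodate possible" correlation within multiple births. The exponentiated treatment coefficient of that model is a risk ratio. The contingency is one clause: if the fit does not "converge, a logistic model will be used". The section does not say which effect measure is then reported, or how a risk ratio would be recovered.

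Section 6.5 repeats the rule for the categorical secondary endpoints ("model does not converge, a logistic model will be used"), and Section 6.6 repeats it for three supplementary binary endpoints. Other sections borrow the Section 6.4 model:

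- Section 7 enters the interaction and main-effect terms as "covariates in the analysis model (as specified in Section 6.4").
- Section 8.1 says that sensitivity to adjustment for "stratification factors will be explored by included them as covariates in the model (See Section 6.4"). Site enters there as tertiles of each site's pooled observed event risk.
- Section 8.2 is written only in relative risk. Its first estimate is "calculated by dividing the estimated relative risk reduction (RRR) by the adherence rate". Its second is a weighted mean of log risk ratios over three site tertiles, each "estimated using the analysis approach specified in Section 6.4) with its corresponding adherence weight to derive a weighted estimate".

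The pooled analyses with the Canadian trial (Section 9.2) follow the same methods. The SAP states no event rate, sample size or target effect for LIFT itself.

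**The concern.** Whether a model converges is a numerical matter, yet under this rule it decides the scale on which a result is reported. A risk ratio and an odds ratio agree closely only when the event is rare, and away from the null the odds ratio lies further from 1.

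Two things follow from the wording. First, Section 8.1 exists to show whether the primary estimate moves when the stratification factors are added. If only the adjusted model falls back, the comparison sets an odds ratio against a risk ratio, and part or all of any shift comes from the scale. Second, the Section 8.2 formulas need a relative risk reduction (RRR) or an RR for each tertile. They take it from an approach that, under the fallback, would return something else.

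**Working it through.** **Inputs.** From the SAP: the log-binomial then logistic sequence (6.4 to 6.6), the covariates of 8.1 and the formulas of 8.2. There is no stated figure to reproduce. Control risk, the RR of 0.80 and the nonadherence below are assumptions.

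**1. Size of the scale change.** With p1 = RR × p0, OR = [p1/(1 − p1)] / [p0/(1 − p0)]. At p0 = 25% and RR 0.80, p1 = 20%, so OR = (0.20/0.80)/(0.25/0.75) = 0.750.

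| Control risk (assumed) | OR for RR 0.80 | 1 − OR | Excess over RRR of 20% (relative) |
|---|---|---|---|
| 10% | 0.783 | 21.7% | 9% |
| 25% | 0.750 | 25.0% | 25% |
| 40% | 0.706 | 29.4% | 47% |

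**2. Which models can fail.** A log-binomial fit runs into trouble when fitted risks are pushed towards or beyond 1.

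- Treatment only (primary, secondary, supplementary binary, adherence tertiles): 2 parameters for 2 cells.
- Treatment by binary subgroup: 4 parameters for 4 cells. Treatment by probiotic-use site tertile: 6 for 6.
- Section 8.1: 1 intercept + 1 treatment + 1 sex + 1 birth weight + 1 plurality + 2 risk tertile = 7 parameters, for 2 × 2 × 2 × 2 × 3 = 48 covariate patterns.

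The first two groups are saturated. Under an independence working correlation, their fitted risks are the observed cell proportions, so the bound at 1 does not bind unless a cell is at 0% or 100%. The Section 8.1 model is not saturated. Its effects multiply, and grouping sites by their own event risk widens the spread of fitted risks.

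**3. Simulation, illustrative only.** Each data set had about 1,500 babies, some in twin pairs, and a true RR of 0.80, with 25 data sets per setting. Cell risks were the nominal risk times 1.6 or 0.5 for birth weight, and times 0.7, 1 or 1.35 for site tertile. The highest control-cell risk is therefore 1.6 × 1.35 = 2.16 times nominal: 0.216, 0.54 and 0.864 at nominal 10%, 25% and 40%. A fit counted as failed if it did not converge or if a fitted risk reached 1.

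- Unadjusted: 150 of 150 converged (3 risks × 2 working correlations × 25). The log-binomial and logistic Wald statistics differed by at most 0.6.
- Adjusted, independence correlation: 0 of 25 failed at 10%, 0 of 25 at 25% and 4 of 25 at 40%. In the converged fits at 40%, the mean RR was 0.81 and the mean adjusted OR 0.63.
- The mean unadjusted OR at 40% was 0.72. So the adjusted OR differs from the primary RR by more than the table suggests, because an odds ratio also moves when prognostic covariates are added, even without confounding.
- In adjusted fits the two Wald statistics differed by up to 16.4 at 40%. The near-equality of the tests belongs to the unadjusted model only.

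A separate check used 500 and 1,500 babies, three pairs of subgroup control risks up to 30% and 85%, two working correlations and 40 data sets each (2 × 3 × 2 × 40 = 480). All 480 two-group fits and all 480 treatment-by-binary-subgroup fits converged.

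**4. Section 8.2 if the fallback fired.** At 25% control risk and an assumed 15% total nonadherence, the formula gives 20%/0.85 = 23.5% from the RRR. Putting 1 − OR in its place gives 25%/0.85 = 29.4%.

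**5. Can an RR be recovered?** Yes. Averaging the logistic model's predicted risks with everyone set to each arm in turn, and taking the ratio, reproduced the unadjusted RR (largest difference 0.000). It came within 0.06 of the adjusted RR wherever the log-binomial model converged.

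**The case against.** The strongest reply is that the rule will almost never operate where it matters. The primary, secondary and tertile analyses contain treatment alone, and the subgroup models are saturated. A reader might infer that the primary result could come out as an odds ratio, that the weighted estimate in Section 8.2 would mix the two measures, or that subgroup tests would show spurious interaction. The planned models do not support those readings as more than theoretical possibilities: each needs a failure in a model that has no realistic reason to fail. That part of the reply stands.

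It is also fair that the fallback is prespecified, so the analyst does not choose it after seeing results. In the unadjusted model, RR = 1 and OR = 1 are the same null hypothesis, so the test is little affected. And Section 8.2 would not be beyond repair, because an RR can be recovered from a logistic fit.

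What the reply leaves untouched is Section 8.1. It is only a sensitivity analysis and feeds no Section 8.2 formula, but its whole purpose is comparison with the primary estimate, and it is the one planned model with a plausible route to failure. Nor does the SAP say that an RR should be recovered, so the reporting scale after a failure is left open.

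**Conclusion.** The point holds in a narrow form and is minor. As written, the rule changes the effect measure without saying so or converting back. In practice the exposure is the adjusted model of Section 8.1. The Section 8.2 formulas are incompatible with the fallback's output on paper, at any event rate, but the fits that feed them should converge.

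The size cannot be fixed from the SAP. It would be tempting to call the composite a common endpoint and quote one inflation figure, but no event rate is given. At an assumed RR of 0.80, 1 − OR overstates the RRR by 9% in relative terms at 10% control risk and by 47% at 40%. How often the Section 8.1 model would fail is equally unknown: failures appeared in the simulation only where the highest cell risk was about 0.86, which nothing in the SAP establishes.

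**What to change.** In Sections 6.4, 6.5 and 6.6, replace the logistic fallback with a rule that keeps the estimand. Suggested text:

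*A risk ratio with 95% CI is reported for every binary endpoint, whichever model is used. If the log-binomial GEE does not converge, or gives a fitted risk of 1 or more, a log-link Poisson GEE with robust variance clustered on the multiple-birth set is fitted instead.*

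An acceptable alternative is a logistic GEE whose predicted risks are standardised over both arms to give a risk ratio, with a confidence interval that respects the multiple-birth clusters. The standardisation route was checked above; the Poisson route was not simulated here. Sections 7, 8.1, 8.2 and 9.2 then inherit the corrected rule, and the Section 8.2 formulas can be used as written. The cost is one sentence in each of three sections, with standard software and no new data.

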6.5 Analysis of Categorical Secondary Endpoints

- 26 Secondary categorical endpoints include: survival to hospital discharge (Section 2.2), brain injury
- 27 (Section 2.3), NEC (Section 2.4), LOS (Section 2.5), RoP (Section 2.6), chronic lung disease (Section
- 28 2.9), and survival and development status at 24-36 months corrected gestational age (Section 2.11).

29

- 30 Secondary categorical endpoints will be analysed using the same modelling approach applied to the
- 31 primary endpoint (i.e. a log-binomial model fitted using generalised estimating equations to
- 32 accommodate possible correlation of data between siblings from multiple births. If the log-binomial
- 33 model does not converge, a logistic model will be used).

- 35 Sensitivity analyses will be undertaken on the categorical morbidity endpoints (i.e. brain injury, NEC,
- 36 LOS, RoP, and chronic lung disease) in which any missing values due to death are treated as an
- 37 event. An analysis of survival to 36 weeks may also be undertaken as a sensitivity analysis. Estimates
- 38 of the treatment effect on survival to hospital discharge that are adjusted for adherence will be
- 39 produced using the methods detailed in Section 8.2 in a sensitivity analysis.

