2.11 Survival and Development Outcomes at 24 to 36 Months Corrected Gestational Age

Major disability is defined as meeting any of the criteria below based on an evaluation performed during the assessment window using the instruments below;

- a modified Short Health Status Questionnaire (SHSQ) completed by a medically qualified practitioner documenting:
- a) major developmental delay, including language or speech problems, or
- b) cerebral palsy with inability to walk unassisted, or
- c) severe visual loss (cannot fixate/ legally blind, or corrected acuity <6/60 in both eyes), or
- d) deafness, requiring a hearing aid or cochlear implants.
- A cognitive composite score from the Bayley-III Scales of Infant and Toddler Development (BSID) indicative of least moderate delay (i.e. a score at least 2 SDs below the age-adjusted norm on the index)
- A problem solving score from the Ages and Stages Questionnaire (ASQ) indicative of least
 moderate delay (i.e. a score at least 2 SDs below the age-adjusted norm on the index. Note
 that a LIFT substudy will, blinded to treatment, compare available BSID data with
 corresponding ASQ data to ensure the chosen ASQ score cut-point corresponds adequately
 well to that for the BSID).

Survival status is collected at discharge and annually thereafter. An infant will be classified as being alive and free from major disability if none of the criteria above are met and adequately complete information is obtained during the assessment window from at least one of the instruments. Any unclear cases (e.g. where only partial information is available, a death occurs after the date of the developmental assessment and before month 36, etc.) will be resolved on blinded clinical review of available information.

1 2.12 Safety

5

6

7

8

9

10

11

12

13

16

23

27

34

- 2 In addition to the morbidity endpoints defined above, safety will be assessed according to the
- 3 incidence of suspected adverse reactions that are classified as serious and unexpected (Suspected
- 4 Unexpected Serious Adverse Reactions SUSARs).

3 Analysis Sets

- The ITT population will comprise all randomised participants.
- The Per Protocol population will comprise all randomised participants that receive least one administration of their assigned treatment and who are not deemed ineligible on blinded clinical review.

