- The safety population will comprise all randomised participants who received at least one administration of assigned treatment. Participants will be analysed according to the treatment they actually received for the purposes of the safety analysis.

Any instances where membership of an analysis set is unclear will be resolved on blinded clinical review. Any exclusions from analysis sets will be documented.

4 Interim and Final Analyses

- 17 The LIFT protocol makes provision for interim analysis of the primary composite endpoint, and of
- survival to discharge, using the Haybittle–Peto approach (see Peto et al¹, Statistical Note No. 4, p.
- 19 611). The procedure involves evaluating the test statistic calculated under null hypothesis against a
- boundary of 3 standard deviations (equivalent to $\chi_1^2 = 9$, with p-value of 0.0027). This has a
- 21 negligible effect on the alpha level applicable at final analysis (i.e. the analysis performed when the
- boundary is not crossed at any interim analysis and the study continues as originally planned).

5 Type I Error (Alpha)

- 24 A two-sided alpha (significance level) of 5% will be applied to the analysis of the primary composite
- 25 endpoint. There will be no adjustment to alpha for interim analyses evaluated using the Haybittle-
- 26 Peto boundary.
- 28 The key secondary endpoints for LIFT comprise the individual components of the primary composite
- 29 endpoint (i.e. survival, brain injury, NEC, LOS, and RoP). P-values adjusted for the five comparisons
- 30 performed for this set of endpoints will be derived using Benjamini-Hochberg procedure² with a
- 31 family-wise error rate of 5%. Results of other endpoint, subgroup, and sensitivity analyses will be
- 32 interpreted in proper context and with due consideration of type I error. The clinical interpretation
- of the statistical evidence from LIFT will take into account the recommendations of Pocock et al^{3,4}.

6 Analysis of Study Endpoints and Patient Characteristics

- 35 Safety analyses will be performed using the safety population. Non-safety analyses will be
- 36 performed using the ITT population. Sensitivity analyses may be performed using the Per Protocol
- 37 population.

1 6.1 Subject Disposition

2 The number of patients in each analysis set will be presented along with reasons for any exclusions.

3 6.2 Baseline Demographic and Clinical Characteristics

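### The SAP sets no missing-data rule for the 24–36 month survival-and-disability outcome; its default analysis over-weights deaths and can bias the treatment effect

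*SAP*

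**What the plan says.** - **Model.** SAP Section 6.5 counts "survival and development status at 24-36 months corrected gestational age (Section 2.11") among the secondary categorical endpoints and says "Secondary categorical endpoints will be analysed using the same modelling approach applied to the" primary endpoint. That means a log-binomial GEE, or a logistic model if it fails to converge. No missing-data method is named.
- **Population.** Under Section 6, non-safety analyses are "performed using the ITT population. Sensitivity analyses may be performed using the Per Protocol" set. Section 3 says "The ITT population will comprise all randomised participants". Neither says what happens to a randomised child whose outcome is missing.
- **Classification.** Under Section 2.11 a child is alive and free of major disability only if no disability criterion is met and "adequately complete information is obtained during the assessment window from at least one of the instruments". Unclear cases, including those with partial data, go to blinded review.
- **Vital status.** Section 2.11: "Survival status is collected at discharge and annually thereafter".
- **Imputation.** Section 6.4: "A multiple imputation approach will be used to account for missing primary endpoint data in a" sensitivity analysis. This concerns the primary endpoint only, as do the optional optimistic and pessimistic scenarios.
- **Other missing-data work in Section 6.5.** The sensitivity analyses name brain injury, NEC, "LOS, RoP, and chronic lung disease) in which any missing values due to death are treated as an" event. The 24–36 month outcome is not on that list.

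**The concern.** A child known to have died needs no developmental assessment to count as an event; the label for the favourable outcome implies this, although the SAP never says it outright. A survivor who is never assessed cannot be classified. A standard GEE uses only records with an observed outcome, so the default fit loses survivors and keeps known deaths. Whether a child is analysed then depends partly on the outcome.

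No other provision fills the gap. Imputation stops at the primary endpoint. The Section 6.5 sensitivity analyses deal with values missing because of death, which is the reverse problem. Blinded review works on available information and cannot classify a child about whom there is none.

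At stake is the effect on survival free of major disability in all randomised babies. In the default set, death counts for more than it should relative to disability. An effect on death alone is exaggerated, an effect on disability alone is diluted, and unequal loss between arms can produce an apparent effect where there is none.

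**Working it through.** The SAP states no event, loss or power figure for this outcome, so there is nothing to reproduce. **All rates below are assumptions.**

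**Notation, per arm:** d = death risk; q = disability risk among survivors; m = share of non-disabled survivors unassessed; m_dis = share of disabled survivors unassessed. All deaths are taken as known.

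- True risk = d + (1−d)q
- Available-data risk = A / (A + B), with A = d + (1−d)q(1−m_dis) and B = (1−d)(1−q)(1−m)

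**1. Over-weighting of deaths.** With d = 0.08 and 20% random loss of survivors, deaths form 0.08/(0.08 + 0.92×0.80) = 9.8% of the analysed set instead of 8%.

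**2. Effect on death only** (d = 0.08 control, 0.06 bLF; q = 0.15 in both).
- True risks: 0.08 + 0.92×0.15 = 0.218 and 0.06 + 0.94×0.15 = 0.201, so RR = 0.922.
- At m = m_dis = 0.20: control (0.08 + 0.1104)/0.816 = 0.2333; bLF (0.06 + 0.1128)/0.812 = 0.2128; RR = 0.912. The risk reduction 1−RR is overstated by 12.8%.

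| m | random loss | m_dis = 1.5m | m_dis = (2/3)m |
|---|---|---|---|
| 10% | 0.917 (+6%) | 0.914 (+11%) | 0.920 (+3%) |
| 15% | 0.915 (+9%) | 0.909 (+17%) | 0.918 (+5%) |
| 20% | 0.912 (+13%) | 0.903 (+24%) | 0.917 (+6%) |
| 30% | 0.906 (+20%) | 0.890 (+41%) | 0.915 (+9.5%) |

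Cells show the available-data RR and, in brackets, the relative change in 1−RR.

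**3. Effect on disability only** (d = 0.08 in both; q = 0.15 vs 0.12). The true RR is 0.1904/0.218 = 0.873. Random loss of 10–30% gives 0.878–0.891, understating the reduction by 4–14%.

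**4. Similar relative effects** (d = 0.08 vs 0.064; q = 0.15 vs 0.12). The true RR is 0.1763/0.218 = 0.809. Random loss of 10–30% gives 0.810–0.813, a change of about 2% or less in the reduction.

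**5. No effect, equal loss.** Both arms have the same formula and inputs, so RR = 1.000 at every loss rate.

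**6. No effect, unequal random loss** (d = 0.08, q = 0.15). The risk is 0.2042/0.908 = 0.22489 at 10% loss and 0.1904/0.816 = 0.23333 at 20% loss. Losing 20% of controls and 10% of bLF gives RR 0.964; the reverse gives 1.038.

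**7. What the fix recovers.** Imputing survivors at the disability rate seen in assessed survivors restores the true RR when loss is random within arm. If loss depends on disability and no predictor explains it, part of the bias stays. In the case of step 2 at m = 0.20:
- m_dis = 0.30: q among the assessed is 0.105/0.785 = 0.1338. RR = (0.06 + 0.94×0.1338)/(0.08 + 0.92×0.1338) = 0.915, against a true 0.922 and an available-data 0.903.
- m_dis = 0.133: q is 0.130/0.810 = 0.1605 and RR = 0.926, against a true 0.922 and an available-data 0.917.

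**The case against.** **A reader might infer that the SAP prescribes a complete-case analysis. It does not.** Complete-case is what a GEE does by default when the text is silent, and the SAP assigns the analysis to all randomised babies. The defect is an unstated rule.

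**A reader might infer that deaths are always known and only survivors go missing.** That is secure only to discharge, where the discharge form records vital status. Later deaths depend on annual follow-up and can be missed in families lost to contact. Section 2.11 also sends a death after the assessment but before month 36 to blinded review. The formula's full ascertainment of deaths is therefore an upper case.

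**A reader might infer that the treatment effect is necessarily biased.** Steps 4 and 5 show otherwise.

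**The shift is small.** At 20% random loss it is ln(0.922/0.912) = 0.011 on the log scale. With an assumed 500 to 1,000 babies per arm, the standard error of the log RR is about 0.13 to 0.09, so the shift is about a tenth of it. The direction of disability-related loss is also open: any one criterion classifies a child as disabled, while disability-free status needs adequate data. Any one of three instruments suffices, and partial cases are reviewed, so missingness is reduced though not removed.

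**Proportion.** This is not one of the five key secondary endpoints. The primary endpoint has the same asymmetry (Section 2.1), and its imputation is only a sensitivity analysis. Requiring imputation as the main analysis of a lesser endpoint is debatable.

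All of this stands as limits on the claim. It does not supply the missing rule, and nobody can know in advance that the effects on death and disability will be proportional or that loss will be equal between arms.

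**Conclusion.** The point holds in conditional form. The SAP names no missing-data method for the 24–36 month outcome and leaves it out of every missing-data sensitivity analysis. The default fit over-weights deaths because they are more completely known than disability. The treatment effect can be biased when bLF acts differently on the two components or when loss differs by arm.

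For the assumed death-only effect, the available-data RR lies between 0.920 and 0.890 against a true 0.922, depending on how much loss there is and whether it relates to disability. For a disability-only effect under random loss, the reduction is understated by 4–14%. These sizes rest entirely on assumed death, disability and loss rates and on complete knowledge of deaths. The documents do not support saying that the estimate will be biased, only that nothing in the plan guards against it. The change is worth making because it is cheap, and the matter is moderate because the endpoint is secondary.

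**What to change.** In SAP Section 6.5, for the 24–36 month endpoint:

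1. State that death before the assessment counts as an event, and state the rule for survivors without an adequate assessment.
2. Extend the multiple imputation of Section 6.4 to this endpoint. Impute disability among those survivors, within arm, from brain injury, treated retinopathy, NEC, late onset sepsis, chronic lung disease, birth weight, gestation, sex, multiple birth and any partial instrument data.
3. Fit the planned GEE to all randomised babies and report it beside the available-data result. Which of the two leads is for the sponsor to settle; both should be prespecified.
4. Add a not-at-random sensitivity analysis, for example with higher and lower odds of disability in unassessed survivors, since step 7 shows imputation alone may not remove loss that depends on disability.

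The cost is SAP wording and one further imputation model on data already collected. The imputation relies on missingness at random given its predictors, which is a weaker assumption than the default analysis needs.
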